12.4.3 Primary Efficacy Endpoint

The primary hypothesis is that TAVI with the TriGuard HDH or TriGUARD 3 system is superior to standard (unprotected) TAVI for the primary hierarchical composite efficacy endpoint of all-cause mortality or any stroke at 30 days (Tier 1), followed by NIHSS worsening (increase from baseline) 2-5 days post-procedure (Tier 2), followed by any ischemic cerebral findings on DW-MRI (Tier 3), followed by total volume of post-procedure cerebral ischemic lesions detected by DW-MRI divided into preset subdivisions (Tier 4). Poolability of the Phase I and Phase II control subjects will be assessed at the time of the primary analysis and the results will determine the control population used for the primary analysis of the primary efficacy endpoint as detailed in the SAP.

The analytic approach is based on the statistical method described by Finkelstein and Schoenfeld.² A similar approach was used in PARTNER Trial (Cohort B) where the co-primary end point was hierarchical composite of the time to death from any cause or the time to the first occurrence of repeat hospitalization (after the index procedure) due to valve-related or procedure related clinical deterioration.¹⁰⁵ In addition, this approach was further explored and recommended for cardiovascular trials by Pocock et al.⁷⁷

In brief, we propose the following analysis methodology:

Each subject in the intervention group is compared with each and every subject from the control group based on the following prespecified hierarchy:

[figure not shown]
- All-cause mortality or any stroke (disabling or non-disabling) [evaluated at 30 days]
 - If both had a death/stroke a time to event analysis by days will determine a win
 - If both patients had a stroke at the same day the comparison moves to the next tier
- NIHSS worsening (increase from baseline) [evaluated at post-procedure (2 to 5 days post-procedure)]
- Freedom from any cerebral ischemic lesions detected by diffusion-weighted magnetic resonance imaging (DW-MRI) 2 to 5 days post-procedure
- Total volume of cerebral ischemic lesions detected by diffusion-weighted magnetic resonance imaging (DW-MRI) 2 to 5 days post-procedure

For example:

- If Subject A has stroke and Subject B survives free of stroke or death to 30 days, Subject B wins (score +1) and Subject A loses (score -1).
- If Subject A and Subject B both have death/stroke, time to event by day will determine a win.
- If both had a stroke on same day, the comparison moves on to the next tier.
- Assuming neither experiences a stroke or death before 30 days, if Subject A experiences NIHSS worsening, and Subject B does not experience NIHSS worsening, Subject A loses (score -1) and Subject B wins (score +1). In case both have NIHSS worsening the patient with the lesser worsening wins.
- Assuming neither subject experiences a stroke or death before 30 days or NIHSS worsening from baseline, if Subject A has no cerebral ischemic lesions on DW-MRI and Subject B has a cerebral ischemic lesion on DW-MRI, Subject A wins (score +1) and Subject B loses (Score -1).
- Assuming neither subject experiences a stroke or death before 30 days, NIHSS worsening from baseline or freedom from DW-MRI cerebral ischemic lesions, if Subject A has a total cerebral ischemic lesion volume of 50 mm³ and Subject B has a total cerebral ischemic lesion volume of 100 mm³, Subject A wins (score +1) and Subject B loses (Score -1).

An illustration of this algorithm is provided in Figure 4 below.

Figure 4. Algorithm of assigning scores by the Finkelstein and Schoenfeld method (*Note: each patient from the intervention group is compared with each and every patient from the control group*)

After all between-subject comparisons have been performed, scores are summed to obtain a cumulative score for each subject, and outcomes between treatment groups are then compared by chi-square test.

This analytic approach does not result in a natural point-estimate (e.g., proportion, mean, median, time-to-event); however, Pocock et al. provided a computational framework for the test statistic called "win ratio". In brief, it is calculated as a proportion of "wins" for each group out of the total number of the pairwise comparisons.

No imputation of missing DW-MRI data will be performed for the primary analysis. However, in order to assess the sensitivity of results to missing DW-MRI data, multiple imputations with the linear regression approach will be used as the secondary sensitivity analysis. This assessment is necessary because the rate of permanent pacemaker implantation (causing loss to DW-MRI follow-up) may vary according to patient clinical characteristics and prosthesis type.¹⁰⁶ Specifically, missing total volume of cerebral ischemic lesions on post-procedure diffusion-weighted MRI will be imputed via multiple imputation linear regression (10 imputed data sets will be created). The covariates used for the imputation model will be treatment group, age at time of enrollment, body mass index, race, smoking status, creatinine level, hyperlipidemia, hypertension, aortic arch disease burden, porcelain aorta, aortic valve area at baseline, procedure time, country, valve type, balloon post dilatation, arch type, and level of calcification. This creation of the 10 datasets will be carried out using PROC MI in SAS. For each data set, the above-mentioned chi-square test will be carried out on the primary endpoint and one overall chi-square result will be generated from the 10 datasets. For each patient with missing TLV, the crux of multiple imputation is to estimate TLV from patients with non-missing TLV who have similar baseline characteristics as the patient with missing TLV. Thus, in essence, TLV for high risk patients with missing TLV due to pacemaker will theoretically be estimated from patients with similar high risk profiles who do not have pacemakers.

The assumptions for powering the primary efficacy endpoint are based on neurologic, and imaging data from a limited number of subjects in the above mentioned RCTs (§12.2.2). In Phase I due to uncertainty regarding the primary efficacy endpoint, an unblinded interim analysis was planned to be conducted to re-evaluate the sample size required to demonstrate superiority of the Intervention group to the Control group. The unblinded interim analysis was planned to be conducted when 90 subjects total who meet the eITT population definition have completed the 30-day follow-up visit. This interim analysis was to be inspected by an independent data safety and monitoring Board (DSMB) and the unblinded results will not be made privy to the sponsor, investigator, or any REFLECT team member, even in the event of a DSMB recommendation of an increase in sample size (i.e., the sponsor will not be made privy to the reason for any DSMB recommendation of an increase in sample size). If the interim analysis would have determined that more than 285 randomized subjects will be required to ensure adequate study power, enrollment would have continued (contingent on DSMB recommendation and prior FDA approval, and at the Sponsor's discretion) until the required number of subjects would have been enrolled, or until the total subject limit for the study has been reached (whichever occurs first).

Specifically, at the interim analysis in Phase I, the trial sample size was to be re-calculated, if necessary, to ensure 80% conditional power to demonstrate superiority (overall 2-sided $\alpha=0.05$) of the Intervention group to the control group for the primary efficacy endpoint, conditioned on the interim unblinded results and loss to DW-MRI follow-up, according to the eITT population definition (there will be no imputation of missing data in this interim analysis; i.e., missing data will be excluded; also, sample size can only be increased at this interim

stage; it will not be decreased beyond what is currently planned). The conditional power and sample size re-calculation for the final analysis were to be ascertained by computer simulations and by established methodology outlined in Chen, DeMets and Lan.¹⁰ i.e., at the interim stage, we were to use Monte Carlo simulations to assess the conditional power of achieving a significant Mann-Whitney test by the end of the study, conditioned on the distribution of the observed interim data. If the conditional power is 50% - 80% (the “promising zone” according to Chen, DeMets and Lan), we were to use simulations to ascertain the increase in sample size required to yield 80% conditional power for the Mann-Whitney test. If the conditional power was determined to be <50% or >80%, the study was to proceed as is without a sample size adjustment (i.e., only the initial randomized cohort of 225 subjects were to be enrolled). The above-mentioned computer simulations were to be carried out assuming the distribution of TLV data follows a negative binomial distribution within each treatment group. The intent of this analysis was to ensure adequate power to detect a clinically meaningful treatment effect at the end of the study by providing the option to increase the sample size if necessary.

There was no intention to stop the study for overwhelming efficacy at the interim analysis. However, as a precautionary measure and to be conservative (due to the presence of an unblinded interim analysis), the O’Brien Fleming alpha spending method was to be used to calculate an alpha penalty for the final analysis regardless of whether a sample size increase is needed (final analysis two-sided alpha = 0.049).

NOTE: A revised adaptive design has been developed for Phase II of the study to inform a potential sample size increase based on interim conditional power; for details, please refer to §12.1.1.

In the final analysis, assessment of treatment-by-study-center and treatment-by-region on the primary efficacy endpoint will be carried out on the eITT population using quantile regression. Total score obtained for each subject using the proposed approach (Finkelstein and Schoenfeld) will be the model dependent variable. The following two models will be built: 1.) Model inclusive of treatment, study center, and treatment-by-study center interaction, and 2.) Treatment region (US versus OUS, Phase I only), and treatment-by-region interaction. A 0.15 level of significance will be used to assess the significance of each of the study center and region effects on the efficacy endpoint. A non-significant result for each of study center and region will support the pooling of patients across study centers and across regions for the primary efficacy analysis. A significant result will require further inspection of the by-center and by-region results to assess if poolability is appropriate. Note that centers with less than 5 subjects will be pooled with other centers by closest geographic region; this pooling will be carried out prior to the unblinding.

Additionally, an assessment of treatment-by-study-center and treatment-by-region on each component of the primary efficacy endpoint will be carried out on the eITT population using analysis of variance on the cube root transformation for total lesion volume data and logistic regression for death/stroke and NIHSS worsening, with effects for 1.) Treatment, study center, and treatment-by-study center interaction, and 2.) Treatment, region (US versus OUS, Phase I only), and treatment-by-region interaction. As above, a 0.15 level of significance will be used to assess the significance of the interaction; a non-significant interaction or an interaction that is significant but only quantitative (and not qualitative) in nature will support the pooling of patients across study centers and across regions for the primary analysis; and centers with less than 5 subjects will be pooled with other centers by closest geographic region, with pooling carried out prior to the unblinding.

In addition, the above analysis will be repeated in the eITT population (separately in Phase I and Phase II analysis sets) to assess the consistency of treatment effects on each component of the primary efficacy endpoint across the following variables:

- Subject gender (male versus female)
- Valve prosthesis type (Edwards vs. Medtronic)
- Operative risk (by Society of Thoracic Surgeons [STS] Risk Score)
- Type and duration of antiplatelet therapy:
 - Pre- and peri-procedural therapy:
 - Protocol-recommended antiplatelet therapy vs. other
 - Maintenance therapy:
 - Dual antiplatelet therapy (DAPT) to 90 days vs.
 - Monotherapy (aspirin or clopidogrel) to 90 days vs.
 - Warfarin with antiplatelet therapy to 90 days vs.
 - Other

As above, analysis of variance on the cube root transformation for total lesion volume data and logistic regression for death/stroke and NIHSS worsening will be used, and a 0.15 level of significance will be used to assess the significance of the interaction.

If the primary efficacy endpoint is met in the primary (eITT) analysis population, sequential testing of the primary efficacy hypothesis will be conducted in the ITT analysis population of evaluable subjects (Roll-In patients are excluded.) As a secondary analysis, the primary efficacy endpoint and its components will be evaluated in the ITT analysis population of evaluable subjects (Roll-In patients are excluded). As an additional analysis, the primary efficacy endpoint will be evaluated in the PT population of subjects with available data.

An additional analysis of the primary efficacy endpoint will also be performed in the primary eITT analysis population with adjustment for pre-existing cerebral lesion volumes. The adjustment will be performed using a quantile regression with the resultant score being the dependent variable and group and the pre-existing cerebral lesion volumes will be independent. Specifically, the PROC QUANTREG procedure will be used to model the median of the score with QUANTILE=0.5 option.

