12.2.1.1.2 Primary Efficacy Hypothesis

The primary hypothesis is that TAVI with the TriGUARD 3 system is superior to standard (unprotected) TAVI for the primary hierarchical composite efficacy endpoint of all-cause mortality or any stroke at 30 days (Tier 1), NIHSS worsening from baseline assessed at 2-5 days post-procedure (Tier 2), freedom from any cerebral ischemic lesions detected by diffusion-weighted magnetic resonance imaging (DW-MRI) 2 to 5 days post-procedure (Tier 3), and total volume of post-procedure cerebral ischemic lesions detected by DW-MRI (Tier 4).

Specifically, the primary efficacy hypotheses are:

H_0 : The hierarchical composite of death/stroke, NIHSS worsening, freedom from any lesions detected by DW-MRI, and larger total lesion volumes is not different between Intervention and Control groups

H_1 : The hierarchical composite of death/stroke, NIHSS worsening, freedom from any lesions detected by DW-MRI, and larger total lesion volumes is lower in the Intervention group than in the Control group

The null hypothesis will be tested at the final analysis at a one-sided 0.025 level of significance. The null hypothesis will be tested using the chi-square test according to the method described in Finkelstein-Schoenfeld² and Pocock⁷⁷.

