To determine the required sample size, calculations were performed by simulating 5000 samples on SAS software postulating the above parameters; mortality and stroke rates and proportions of patients with NIHSS worsening, any MRI lesions and volumes divided to subsets were simulated by a random binary function.

An evaluable sample size of 225 subjects (2:1 randomization with 150 in the Intervention group and 75 new Control subjects) is sufficient to demonstrate superiority of the Intervention group to the Control group for the primary efficacy endpoint when pair-wise comparisons are made between subjects using the Finkelstein-Schoenfeld method,² and outcomes between treatment groups are compared by the chi-square test.

Therefore, the initial randomized cohort sample size of 225 subjects (150 in the Intervention group and 75 new control subjects) will have >80% power to demonstrate superiority of the Intervention group for the primary efficacy endpoint (one sided $\alpha=0.025$). Notably, in several simulations, considering different distributions for lesion volume and different distributions for death/ stroke, the study power remained greater than 80%.

Adding the 63 control subjects already enrolled in REFLECT Phase I for a total of 138 control subjects would increase the power to at least 92% to demonstrate superiority of the primary efficacy endpoint. 5% loss to follow up is included.

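### Section 12.4.3 defines the win ratio as each group's share of all pairwise comparisons, so the effect size described for the primary endpoint has the wrong formula for its label

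*Combined protocol and SAP*

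**What the plan says.** Section 12.4.3 scores every Intervention–Control pair through the four tiers and sums the scores for each subject; "outcomes between treatment groups are then compared by chi-square test". It then concedes a limitation: "This analytic approach does not result in a natural point-estimate". To fill the gap it turns to a cited methods paper which, it says, "provided a computational framework for the test statistic called 'win ratio". The formula follows as a short summary: "it is calculated as a proportion of 'wins' for each group out of the total number of the pairwise comparisons".

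The decision rule is stated separately in section 12.2.1.1.2: "The null hypothesis will be tested at the final analysis at a one-sided 0.025 level of significance", using the chi-square test according to two cited methods papers. Section 12.2.4.1.2 says that 150 Intervention and 75 new Control subjects "will have >80% power to demonstrate superiority of the Intervention group for the primary efficacy endpoint", and that adding 63 Phase I controls "would increase the power to at least 92% to demonstrate superiority of the primary efficacy endpoint".

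Nowhere does section 12 divide one group's wins by the other's, give a null value for the win ratio, say how ties enter it, or attach a confidence interval to it. Sections 12.1 and 12.4.3 refer to a separate SAP for further detail; its text is not in the documents.

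**The concern.** A ratio of wins has a natural reference value of 1, with benefit above it. A share of all pairs can never be above 1, however effective the device. Because ties stay in the denominator, the share also changes with anything that changes the number of undecided pairs, even when the balance of wins and losses is the same. The plan expects many undecided pairs: it assumes 15% loss to MRI, does not impute missing MRI in the primary analysis, and sets a minimum volume difference for a win in Tier 4.

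This sentence is the only unadjusted effect measure described for the primary endpoint. If it is programmed literally, the report would show a number under a familiar name that does not mean what the name says.

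**Working it through.** The documents state no numerical win ratio, so there is none to reproduce. The check has four steps.

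**1. Algebra.** Let N be the number of pairs, W those won by the device, L those won by control, and T the ties, so W + L + T = N.

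- Plan's formula: device W/N, control L/N.
- Win ratio: W/L = (W/N) ÷ (L/N), because N cancels.
- With no treatment effect W = L, so the win ratio is 1 but the plan's quantity is (1 − T/N)/2. With 32.2% ties that is (1 − 0.322)/2 = 0.339. The null value of the plan's quantity therefore depends on the tie rate.

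**2. Effect of ties alone.** Hold the win ratio at 1.81. Then W/N = (1 − T/N) × 1.81/2.81 = (1 − T/N) × 0.644.

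- No ties: 0.644
- 29.2% ties: 0.708 × 0.644 = 0.456
- 37.0% ties: 0.630 × 0.644 = 0.406

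The treatment contrast is the same, but the value the plan would call the win ratio differs.

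**3. Ties from missing MRI.** From section 12.2.4.1.2, with MRI missing independently in 15% of subjects, 1 − 0.85² = 27.75% of pairs lack at least one scan. Pairs in which neither subject has a Tier 1 or Tier 2 event make up 0.89 × 0.91 × 0.94 × 0.94 = 71.6%. If such pairs with a missing scan score 0, ties from this source alone are about 0.2775 × 0.716 = 20% of all pairs. Scoring them 0 is an assumption: the plan says only that missing MRI is not imputed.

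**4. Simulation under the plan's rates.** Inputs from section 12.2.4.1.2:

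- Tier 1: 11% control, 6% device
- Tier 2: 9% and 6%
- Volume categories 0, >0–50, >50–150 and >150 mm³: 11/7/33/48% control, 27/19/7.5/46% device
- 30% volume reduction, on or off
- Minimum difference of 15% or 50 mm³, taken as either or as both
- 15% missing MRI and 5% other loss

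Assumptions not in the documents: event day uniform over 0–30; NIHSS worsening uniform over 1–4 points; volume uniform within category, with the top category capped at 300 or 1,000 mm³; missing data tied at that tier. Win fractions come from 3,000 × 3,000 pairs, and power from 1,000 replicates at z > 1.96.

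| Cap (mm³) | 30% reduction | Threshold | Device W/N | Control L/N | Ties | W/L | Power 150:75 | Power 150:138 |
|---|---|---|---|---|---|---|---|---|
| 300 | no | either | 0.415 | 0.262 | 0.322 | 1.58 | 62.8% | 75.6% |
| 300 | no | both | 0.398 | 0.232 | 0.370 | 1.72 | 58.7% | 75.4% |
| 300 | yes | either | 0.468 | 0.232 | 0.300 | 2.01 | 95.8% | 99.9% |
| 300 | yes | both | 0.439 | 0.195 | 0.366 | 2.25 | 96.9% | 99.3% |
| 1,000 | no | either | 0.425 | 0.270 | 0.305 | 1.57 | 60.3% | 71.5% |
| 1,000 | no | both | 0.427 | 0.262 | 0.311 | 1.63 | 57.8% | 71.5% |
| 1,000 | yes | either | 0.448 | 0.260 | 0.292 | 1.72 | 87.1% | 95.8% |
| 1,000 | yes | both | 0.436 | 0.241 | 0.322 | 1.81 | 81.0% | 93.4% |

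The four rows with the 30% reduction agree with the plan's power statements of more than 80% and at least 92%, so they are the closest to its own scenario. There the formula gives 0.44–0.47 for the device against a wins-to-losses ratio of 1.72–2.25. In the last row, with 150 × 75 = 11,250 pairs, the device wins about 0.436 × 11,250 = 4,905 and control about 0.241 × 11,250 = 2,711. The ratio is 4,905/2,711 = 1.81; the plan's formula prints 0.44.

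**The case against.** The strongest defence is that the sentence gives a proportion for each group. Two proportions over the same denominator, say 0.44 and 0.24, show plainly which group won more, and their quotient is the win ratio. That stands, and it limits the point. A reader might infer that an effective device would be reported as harmful, or that the result could not be compared with other win ratios. The documents do not support either inference: they do not say that one group's value will be printed alone against a null of 1, and the correct ratio is one division away.

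Second, the sentence is a brief paraphrase of a named method, the text calls the quantity a test statistic, and it does not expressly commit to reporting it. A careful programmer might follow the cited paper instead. That is possible, but the sentence is offered where a point estimate is missing, and it is the only formula given.

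Third, a reader might infer that the plan has no other effect estimate and no confidence interval. That goes too far. Section 12.4.3 adds a median-score quantile regression adjusted for pre-existing lesion volume, and the hypothesis-driven secondary endpoints have their own group comparisons. The separate SAP may define the win ratio correctly and give an interval. One can say only that section 12 gives none for it. If the SAP does define it correctly, the protocol sentence disagrees with it and still needs changing.

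**Conclusion.** The point holds as an error of definition and labelling. That the formula is a proportion, cannot exceed 1 and falls as ties rise for a given win ratio is arithmetic and needs no assumption. The size does need assumptions: across the eight scenarios the formula gives about 0.40–0.47 for the device and 0.20–0.27 for control, against wins divided by losses of about 1.6–2.25. Those ranges depend on the volume distribution, the reading of the 15%/50 mm³ rule, the scoring of missing MRI as ties, and whether the 30% reduction applies.

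Trial success is unaffected. It rests on the Finkelstein-Schoenfeld chi-square test for efficacy together with the safety endpoint, and neither test uses this quantity.

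**What to change.** Replace the sentence in section 12.4.3 with: *win ratio = number of pairs won by the Intervention group divided by number of pairs won by the Control group (ties excluded from the ratio, null value 1), reported with a 95% confidence interval.* Report the win, loss and tie percentages alongside, so that the share of undecided pairs is visible. Stop describing the win ratio as the test statistic, and state that the test is the Finkelstein-Schoenfeld chi-square test. Check that the separate SAP carries the same definition.

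Net benefit and a breakdown by tier would be useful additions, but they are reporting practice and not part of correcting this error.

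The cost is one sentence and standard code. Enrolment, alpha, sample size and the primary test do not change. The edit should be made before unblinding so that the effect measure is prespecified.

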12.2.4.1.2 Primary Efficacy Endpoint

Sample size for assessing superiority of Intervention over Control with respect to the hierarchical composite primary efficacy endpoint was estimated using the following assumptions:

- All-cause mortality or any stroke at 30 days will occur in ~11% of Control subjects and ~6% of Intervention subjects (5% absolute reduction, ~45% relative reduction)
- Among subjects without all-cause mortality or any stroke to 30 days, NIHSS worsening 2-5 days post-procedure will occur in 9% of Control subjects and 6% of Intervention subjects (3% absolute reduction, 33.3% relative reduction)
- Among subjects without all-cause mortality or any stroke to 30 days and without NIHSS worsening 2-5 days post-procedure, MRI findings will occur in 89% of Control subjects and in 73% of intervention subjects (16% absolute reduction, 17.9% relative reduction).
- Among subjects without all-cause mortality or any stroke to 30 days, without NIHSS worsening 2-5 days post procedure, but with MRI findings, lesion volumes can be divided into 3 out of 4 subsets- 0 mm³, >0-50 mm³, >50-150 mm³ and >150 mm³. For these volume subsets, we expect rates of 11%, 7%, 33% and 48%, respectively, in the control group and 27%, 19%, 7.5%, and 46%, respectively, in the intervention group.
- For sample size calculations a relative reduction of 30% is expected in each lesion volume subset, based on the comparison of total lesion volumes between device and control groups in DEFLECT I, MISTRAL C⁷³ SENTINEL⁹ and CLEAN-TAVI⁷⁴.
- The smallest detectable difference in MRI is a single voxel. In addition, inter-rater mean differences between two independent observers was 15% or ~5 voxels (40.5 mm³) in the KSH Methodology/Reproducibility Study (data on file). Accordingly, a meaningful difference to declare a win/lose between MRI lesion volumes was set at a 15% relative difference or a 50 mm³ absolute difference.

- Loss to post-procedure DW-MRI follow-up is expected to occur in 15% of all subjects (due to contraindications to post-procedure DW-MRI [e.g., pacemaker implantation] or subject non-compliance)
- Loss to follow-up for all other reasons is expected to be 5%.
- Overall α (one-sided)=0.025; (see §12.4.2)

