12.4.2 Primary Safety Endpoint

The primary safety hypothesis is that the rate of the Combined Safety Endpoint (defined according to VARC 2 as the composite of death, stroke, life-threatening or disabling bleeding, AKI [Stage 2/3], coronary artery obstruction requiring intervention, major vascular complication, and valve-related dysfunction requiring repeat procedure) at 30 days in the group undergoing TAVI with the TriGuard HDH or TriGUARD 3 system (Intervention group) is significantly less than the Performance Goal (PG). The following analysis will be carried out in the AT (primary analysis population) and ITT populations including Roll-ins.

The primary safety analysis will assess if the Intervention group's safety endpoint rate is significantly less than 34.4% using a one-sample z-test of proportions. Specifically, the null and alternative hypotheses to be tested are:

$$H_0: \pi \geq 0.344$$

$$H_1: \pi < 0.344$$

where π is the true, unknown, safety event rate for the Intervention arm.

The number and percentage of patients in each group experiencing the safety endpoint rate will be presented for each treatment; in addition, one-sided 95% confidence intervals of the percentage will be presented, based on the normal approximation to the binomial distribution. For the intervention group, the above null hypothesis will be carried out at a one-sided 0.05 level of significance using the one-sample z-test of proportions. Only AT and ITT patients who experienced a safety endpoint or had at least 23 days (30 days minus the allowable 7 day visit window) of follow-up will be included in the analyses.

As a secondary analysis, to account for any missing data in the primary endpoint (caused by not experiencing the safety endpoint AND prematurely withdrawing from the study before 23 days of follow-up), a tipping point analysis will be conducted. Here the above safety null hypothesis will be repeatedly tested, first assuming 0 patients with missing data failed (i.e., experienced the safety event), then assuming 1 patient with missing data experienced the safety event, then assuming 2 patients with missing data experienced the safety event, etc. Of interest is the "tipping" point, i.e., the number of Intervention missing data subjects who must be imputed as failures in order for the safety null hypothesis to no longer be rejected.

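### The one planned sensitivity analysis for missing DW-MRI in the primary efficacy endpoint assumes missing at random, so it cannot show whether a positive result depends on that assumption

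*Combined protocol and SAP*

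**What the plan says.** Section 12.2.4.1.2 plans for substantial scan loss: "Loss to post-procedure DW-MRI follow-up is expected to occur in 15% of all subjects". It names contraindications such as a new pacemaker, and non-compliance, as the causes.

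Section 12.4.3 does not impute missing DW-MRI in the primary analysis. It then says that, "in order to assess the sensitivity of results to missing DW-MRI data, multiple imputations with the linear regression approach will be used". Ten data sets are created in PROC MI. Total lesion volume (TLV) is modelled from treatment group and 16 other covariates, among them valve type, procedure time and calcification. The section states its own assumption: "TLV for high risk patients with missing TLV due to pacemaker will theoretically be estimated from patients with similar high risk profiles", meaning patients without a pacemaker.

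For the primary safety endpoint, where 12.2.4.1 expects 5% loss, section 12.4.2 goes further: "a tipping point analysis will be conducted". No counterpart is given for efficacy. The eITT, ITT and Per Treatment analyses, and the adjustment for pre-existing lesion volume, change the population or the model. They do not change what is assumed about unscanned subjects.

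**The concern.** The analysis is meant to show how far the efficacy result depends on missing scans. A model with treatment group among its predictors, fitted to scanned subjects, assumes that an unscanned subject has the lesion volume expected of a scanned subject in the same arm with the same covariates. The trial cannot check this, because those subjects have no scan.

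Such a model passes the device advantage seen in scanned subjects on to unscanned ones. Agreement with the primary analysis is then close to built in at the planned effect, and says little about the case that matters: unscanned device subjects doing worse than scanned ones. What is at stake is the robustness statement in the final report, not the primary p-value.

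**Working it through.** **Inputs from the plan.**
- Test level (12.2.1.1.2): "The null hypothesis will be tested at the final analysis at a one-sided 0.025 level of significance".
- Size (12.2.4.1.2): "2:1 randomization with 150 in the Intervention group and 75 new Control subjects", or 138 controls once the 63 from Phase I are added.
- Rates, control v device (12.2.4.1.2): death or stroke 11% v 6%. NIHSS worsening among the rest 9% v 6%. Volume bands 0, >0-50, >50-150 and >150 mm³: 11/7/33/48% v 27/19/7.5/46%.
- Also from 12.2.4.1.2: a 30% volume reduction within each band, a win margin of 15% or 50 mm³, 15% MRI loss and 5% other loss.

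**Assumptions added here.** A pair lacking a scan scores 0 at Tiers 3-4. Event days are uniform over 30 days and the size of NIHSS worsening is geometric. Volumes are uniform within the bounded bands, with an exponential (mean 300) or half-lognormal tail above 150 mm³.

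**Step 1: the plan's power.** The plan says 225 subjects "will have >80% power to demonstrate superiority of the Intervention group for the primary efficacy endpoint", and that the Phase I controls "would increase the power to at least 92% to demonstrate superiority of the primary efficacy endpoint". A Monte Carlo of the four-tier Finkelstein-Schoenfeld test (1,500 runs per setting) gives 84-86% and 94-96%, so both statements reproduce. Without the 30% reduction, power is only 56-62% and 70-75%. The reduction is therefore part of the planned effect and is kept below.

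**Step 2: pairs undecided for lack of a scan.**
- Device subject clear of Tiers 1-2: 0.94 × 0.94 = 0.8836.
- Control subject clear of Tiers 1-2: 0.89 × 0.91 = 0.8099.
- Pair reaches the MRI tiers: 0.8836 × 0.8099 = 0.7156.
- At least one scan missing: 1 − 0.85² = 0.2775.
- Product: 0.7156 × 0.2775 = 0.199, about 20% of all pairs.

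This ignores the few ties within Tiers 1-2 and the 5% other loss.

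**Step 3: what the planned imputation does.** Ten imputed data sets came from a regression on treatment and eight simulated covariates (standing in for the 16), pooled by Rubin's rules. Three versions were run: raw volume truncated at 0, cube root, and a within-arm draw. There were 400 trials per main setting, 250 for the shifts, and a further 700 at the planned effect with 150 v 75. The table gives the share of significant primary results that lose significance.

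| Scenario | 150 v 75 | 150 v 138 |
|---|---|---|
| Scans missing at random: planned imputation | 0.2-3% | 0-0.3% |
| Unscanned device subjects all >150 mm³: complete data | 27% | 17% |
| Same truth: planned imputation | 1-3% | 0-0.3% |
| Imputed device volumes ×1.5 | 3-4% | 0-0.4% |
| Imputed device volumes ×2 | 5-7% | 1-2% |
| Imputed device volumes ×4 | 13-16% | about 6% |
| Extreme bound: unscanned device worst, unscanned control lesion-free | 93-94% | 90-93% |

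The 27% rests on 0.840 × 400 = 336 significant trials, so its standard error is √(0.27 × 0.73 / 336) = 2.4 points. For the 17%, 0.958 × 400 = 383 trials give 1.9 points.

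The mechanism shows in the effect size. In a separate run of 800 trials at 150 v 75, within-arm draws raised the mean net benefit from 0.21 to 0.26.

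**Step 4: away from the planned effect.** With 150 v 75 and a weaker effect (power about 34%), the imputation overturns 2-15% of significant results. Under the null it overturns about a quarter of chance positives. These results lie near the boundary and tip over when the data are perturbed. The missing-at-random assumption is not being tested.

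**The case against.** The plan does limit the more obvious informative missingness. Most pairs with a death, a stroke or a differing NIHSS outcome are decided before the MRI tiers. The eITT population removes conversion to surgery and prolonged cardiac arrest before the scan. Section 12.4.3 ties pacemaker rates to patient characteristics and prosthesis type, and valve type is both a randomization stratum and an imputation covariate. Nothing in the text suggests that unscanned device subjects have larger lesions than unscanned controls, so the one-sided scenarios above are the reviewer's. All of this stands. It makes missing at random more plausible, but it does not test it. Non-compliance is also a listed cause of scan loss, and section 6.3 does not list the implanting operators among those blinded, so scan loss unrelated to arm cannot be taken for granted.

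The tie rule is also an assumption: 12.4.3 says only that nothing is imputed, and the algorithm figure is not shown. If subjects without a scan were instead left out entirely, 1 − 0.85² = 27.75% of pairs would involve one, so the gap does not depend on the tie rule.

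That this is the only such analysis can be said of the supplied text alone. Sections 5.1.1, 12.1 and 12.4.3 refer to a SAP for detail, and nothing beyond section 12 is available here.

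Two stronger readings are tempting. A reader might infer that any positive result will be confirmed. That holds only near the planned effect (Step 4). A reader might also infer that the efficacy result is fragile, pointing to the loss of more than 90%, or to a 38% loss when volumes are doubled and no unscanned device subject is lesion-free. The first is a bound built to fail. The second stacks two departures and drops the 30% reduction; with the reduction it is 15%. Neither describes the plan's own scenario.

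**Conclusion.** The point holds in a limited form. In the supplied text, the only sensitivity analysis for missing DW-MRI in the primary efficacy endpoint is a missing-at-random imputation, which cannot reveal dependence on that assumption. The clearest evidence is the contrast when unscanned device subjects all have lesions above 150 mm³. Complete data would overturn about 27% of significant results (17% with 138 controls), while the imputation overturns 1-3% (0-0.3%).

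Moderate departures do little harm at the planned effect, so the result may well prove robust. The plan as written could not show it. The sizes rest on the planned rates with the 30% reduction, scan loss of 15% in each arm, ties for pairs lacking a scan, and simulated covariates in place of the real ones. This is worth changing, but it does not threaten the primary test.

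**What to change.** In 12.4.3:

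1. Keep the multiple imputation as the base case, but impute in two steps: lesion present or absent by logistic regression, then volume among lesion-positive subjects, for example on the cube-root scale that the section already uses for TLV. A linear model of volume gives no exact zeros, so without this step the Tier 3 status of an imputed subject is undefined.
2. Add a prespecified delta-adjusted tipping-point analysis, in line with 12.4.2. Shift the imputed device-arm lesion-free share and the imputed device-arm volume over a stated grid, separately and together.
3. Include one run that draws missing device subjects from the control-arm distribution given covariates.
4. Report the shift at which the one-sided p-value first exceeds 0.025. Call the efficacy result robust to missing MRI only if it stays significant in the control-distribution run.
5. State how a pair lacking a scan is scored at Tiers 3-4.

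The cost is plan wording and some programming, with no new data. The robustness statement may become less favourable. The primary test and alpha do not change.
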